1.2 Trial Objectives

Primary Objective

The primary objective of this study is to assess the efficacy of dietary supplement NR on shortening recovery time after critical illness.

Secondary Objectives

The secondary objectives of this study are:

- To assess the effect of NR on mortality
- To assess NR adverse events
- Other secondary objectives are described in the protocol but will not feature in the main publication

2 Trial Methods

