2.4 Statistical Framework

The statistical framework will be based on the context of dose-finding, for which there are two main approaches: "regression" and "contrast" (Senn, 2007). In the regression approach, the actual doses used in the trial are viewed as samples from a dose continuum, and the purpose is to estimate the dose response curve. In the contrast approach, interest is on one or (more likely) several contrasts between the doses used in the trial. The former is the most explorative and may be sensitive to modeling choices, small number of doses, and over-fitting, especially for small sample sizes (such as in this trial). The latter is well suited for determining the *minimum effective dose*, in which we compare the different doses to placebo.

Specification of the Primary Objective

The primary objective of this study will be to establish the minimum effective dose of NR on shortening recovery time after critical illness. The primary outcome is length of hospital stay in days (see Section 5.1 for details).

There is only one identified primary analysis in this trial. All other efficacy analyses will be regarded as supportive or exploratory.

Hypothesis Setup

Let μ_1 , μ_2 , μ_3 , and μ_4 denote the mean lengths of hospital stay for placebo, low dose (250 mg/day), medium dose (500 mg/day), and normal dose (1 g/day), respectively.

The statistical scheme to account for multiple testing is based on the *closed multiple test procedure* of Marcus et al. (1976). Under the monotonicity assumption, we define a set of elementary null hypotheses (the many-one comparison) with a preassigned order of performing the tests (Williams, 1971):

Step 1: Test the null hypothesis H_0 : $\mu_1 = \mu_4$ Step 2: Test the null hypothesis H_0 : $\mu_1 = \mu_3$ Step 3: Test the null hypothesis H_0 : $\mu_1 = \mu_2$

The test in Step 1 is carried out with a nominal significance level of α = 0.05. If the test is rejected, the test in Step 2 can be carried out, also with α = 0.05. If the test in Step 2 is rejected, the test in Step 3 can be carried out (with α = 0.05). The tests in steps 2 and 3 are only performed if the preceding null hypothesis is rejected, which – together with the monotonicity assumption – ensures that the significance level is preserved for the entire procedure (Williams, 1971; Bauer, 1991). All tests will be performed two-sided.

Decision Rule

The testing scheme above can result in four situations:

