- 1. The null hypothesis in Step 1 is not rejected. Decision: No effect of NR for the doses in the study.
- 2. The null hypothesis in Step 2 is not rejected. Decision: The normal dose is the minimum effective dose.
- 3. The null hypothesis in Step 3 is not rejected. Decision: The medium dose is the minimum effective dose.
- 4. The null hypothesis in Step 3 is rejected. Decision: The low dose is the minimum effective dose.

Assumption

The dose response is assumed to be monotone, i.e., the effect of low dose is less than or equal to the effect of medium dose, which is less than or equal to the effect of normal dose. Or, consequently, that the mean length of hospital stay decreases monotonous from placebo (μ_1) to normal dose (μ_4):

 $\mu_1 \ge \mu_2 \ge \mu_3 \ge \mu_4$.

Adaptation to Estimation

Hypothesis testing will only be performed for the primary outcome. For all secondary outcomes, estimation of treatment effect with 95% (two-sided) confidence intervals will be carried out instead of hypothesis testing in each of the three steps described above. The overall statistical approach will be the same; however, the criterion for performing steps 2 and 3 is that the 95% confidence interval from the preceding step does not contain the null effect value.

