3.1 Confidence Intervals and P-values

All calculated *P*-values will be two-sided and compared to a 5% significance level. If a *P*-value is less than 0.05, the corresponding treatment group difference will be denoted as statistically significant. All efficacy estimates will be presented with two-sided 95% confidence intervals. The statistical approach to account for multiple testing of three doses versus placebo is the closed multiple test procedure (see Section 2.4). As there is only one primary null hypothesis setup to be tested in this trial, there will be no further adjustments for multiplicity.

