4.3 Baseline Patient Characteristics

 The patient demographics and baseline characteristics to be summarized include age in years, gender, ethnicity, body mass index, type of accommodation/level of care before admission, smoking status, level of frailty, Charlston score, in-hospital level of care, type of treatment during hospital stay (pressor, respiratory support, 02 supply), diagnosis, SAPSscore, degree of inflammation (highest CRP), mortality and morbidity (number of new organ failures).

Patient demographics and baseline characteristics will be summarized by randomised treatment arm and overall using descriptive statistics for continuous variables, and number and percentages of patients for categorical variables. There will be no statistical analysis of treatment difference. Any clinical important imbalance between the treatment groups will be noted.

5 Definitions of endpoints and Other Variables of Interest

Primary endpoint

Length of Hospital Stay

The length of hospital stay is defined as the number of days from commencing study treatment to medically fit for discharge from the hospital (to home, long term care facility or rehabilitation center or other facility with a lower care level). The term "Medically fit for discharge" is used instead of "discharge" to correct for extended stays due to logistical challenges (Example: medically fit for discharge, but no availability in long term facilities at that time). Only one patient was not discharged on the same day as she/he was medically fit for discharge). Admission to other hospitals after transfer from the first will be included in the total length of stay. The primary outcome will be the time from start of study treatment to discharge. Patients who die before discharge will be censored at the time of death.

Secondary endpoints (safety)

All-cause Mortality

All-cause mortality is a time to event outcome, with the date of randomization as the time when a patient becomes at risk. If a patient does not die during the study's follow-up, the observation is censored at the patient's last automated follow up.

New Infections

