New infections is defined as any infection, mild or serious, occurring between the last point of contact to the next i.e. if a patient has an upper airway infection after discharge, but before the 90 day follow up appointment, this will count as one new infection at the 90 day follow up appointment. The outcome will be the number of new infections per patient, which is a discrete numerical variable.

Re-admissions

Re-admissions is defined as number of all-cause hospital admissions, surgical and medical, up until end of study. The outcome will be the number of new admissions per patient, which is a discrete numerical variable.

Other variables of interest

Metabolites

Rise in NR metabolites from inclusion to day 7 (or discharge if discharged prior to day 7) and until day 90.

Table 1: Overview of outcomes to be reported in the main article. Outcomes to be presented in subsequent articles are listed and defined in the protocol but not shown here.

Level	Outcome	Timeframe	Туре
Primary	Length of hospital stay (to medical fit for discharge)	65 weeks	Time to event
Secondary	Change in grip strength	90 days	Continuous (change from baseline)
	Change in grip strength	7 days	Continuous (change from baseline)
	All-cause mortality	-	Time to event
	Number of new infections per patient	65 weeks	Discrete numerical
	Number of re-admissions per patient	65 weeks	Discrete numerical

6 Statistical Analysis Methods

The overall statistical approach is presented in Section 2.4 and involves 1-3 steps of hypothesis testing and/or estimation of treatment effect. In step 1, only the patients in the normal dose group of NR will be used (in addition to the patients in the placebo group); in Step 2, only the patients in the medium dose group will be used; and in step 3, only the patients in the low dose group will be used. This approach will be followed for the primary and all secondary outcomes. The statistical methods for steps 1-3 will be presented for each type of outcome in the following subsections.

As an exploratory analysis, we will also perform an overall vs. placebo analysis, where the low, medium, and normal dose groups are combined and compared with placebo.

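### For every secondary outcome, including the three headed as safety, the SAP gives the 500 and 250 mg/day effect estimates only if the preceding dose's 95% CI excludes the null

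*SAP*

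**What the plan says.** SAP 2.4 sets three ordered steps for length of stay: placebo against 1 g/day, then 500 mg/day, then 250 mg/day, each taken only if the one before rejects. Under Adaptation to Estimation it then states that "Hypothesis testing will only be performed for the primary outcome". Secondary outcomes get estimates with 95% CIs, but the "criterion for performing steps 2 and 3 is that the 95% confidence interval from the preceding step does not contain the null" value.

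The introduction to SAP 6 confirms the scope: "This approach will be followed for the primary and all secondary outcomes". Each step uses placebo and one dose group, so the 500 mg/day effect estimate exists only in step 2 and the 250 mg/day estimate only in step 3. Sections 6.2 (grip strength), 6.3 (mortality) and 6.4 (new infections, re-admissions) all work step by step. SAP 5 lists the last three outcomes under a safety heading, and no exception is made for them.

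On error control, SAP 2.4 says "All other efficacy analyses will be regarded as supportive or exploratory" and SAP 3.1 says "there will be no further adjustments for multiplicity". On the dose ordering, SAP 2.4 says "The dose response is assumed to be monotone", but the inequality that follows is written for mean length of stay only.

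**The concern.** An ordered gate keeps the error rate of a sequence of tests at its nominal level. The SAP declares no tests and no error rate for the secondary outcomes, so here the gate has nothing to protect. What it does is decide, from the result at one dose, whether the effect at another dose is estimated at all.

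SAP 1.2 makes this a stated aim of the trial: "To assess the effect of NR on mortality". Yet the mortality HR at two of the three doses depends on whether another dose reached significance. The gate looks only at 1 g/day against placebo, so a difference confined to 500 mg/day would almost never receive an estimate. The same 18 placebo patients enter every step, so a chance low or high placebo result that opens the gate also shifts the 500 mg/day estimate that is then reported.

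**Working it through.** The plan gives no figure for how often steps 2 and 3 would be reached on a secondary outcome, so there is none to reproduce. Its 80% power concerns the primary dose-response test.

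**Inputs.** Group sizes are from SAP 2.1 and 2.3: placebo 18, 1 g/day 20, 500 mg/day 10, 250 mg/day 10. CIs are two-sided 95%. Effect sizes and mortality rates below are assumptions.

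**Normal outcome, SD 1: structure of the gate**
- SE of 1 g/day v placebo: √(1/18 + 1/20) = 0.325.
- SE of 500 mg/day v placebo: √(1/18 + 1/10) = 0.394.
- Correlation through the shared placebo group: (1/18)/(0.325 × 0.394) = 0.43.

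**No effect at any dose** (simulated, t intervals)
- Step 2 is reached in 5.0% of trials and step 3 in 0.8%.
- With no effect, a 500 mg/day CI that misses the truth is one that excludes zero, so step 3 is reached exactly when step 2 is reached and its CI misses. The miss rate when shown is about 0.8/5.0, or 15 to 16%, so coverage is about 85% (simulation 84 to 85%).

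**True 0.5 SD at 1 g/day and 500 mg/day**
- Signal in step 1: 0.5/0.325 = 1.54. With known variance the gate opens with probability P(Z > 1.96 − 1.54) = 34%; with t intervals, 32%.
- Given that the gate opened, the step 1 z-statistic exceeds its mean by 1.08 on average. Through the shared placebo group this moves the 500 mg/day estimate by (1/18)/0.325 × 1.08 = 0.171 × 1.08 = 0.18 SD.
- The reported estimate therefore averages 0.5 + 0.18, or 0.68 to 0.69 SD in simulation. Coverage is about 94%.
- If 0.5 SD is true at 1 g/day only, the reported 500 mg/day estimate averages 0.18 SD when the truth is 0, again with coverage of about 94%.

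**Counts** (Welch interval, assumed placebo means 0.3 to 1.0, Poisson and negative binomial, no effect): step 2 is reached in 4.3 to 5.0% of trials, with coverage of 85 to 90% when shown.

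**Mortality** (Cox model, Wald CI, common follow-up; an arm with no deaths counts as gate closed). Protocol 1.4.1 cites one-year mortality of 17% and 30% in matched non-weak and weak ICU patients. The 10% row is added because this trial also recruits from regular wards and excludes patients expected to die within 90 days. None of these is a rate for this trial.

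| Assumed placebo mortality | 500 mg/day HR produced, no effect | 500 mg/day HR produced, HR 2 at 1 g/day | 250 mg/day HR produced, HR 2 at both higher doses |
|---|---|---|---|
| 10% | 0.07% | 1% | 0.03% |
| 17% | 0.7% | 8% | 1.2% |
| 30% | 2.8% | 22% | 7.8% |

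With assumed staggered follow-up (4, 3 and 1.5 years for phases 1, 2 and 3, and the same rates per year), the two 500 mg/day columns become 0.4 to 4.1% and 5 to 31%. At 17 to 30% mortality with no effect, the 500 mg/day HR interval still covers the truth 93 to 99% of the time when shown, because with so few deaths it is conservative.

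**The case against.** The strongest case on the other side has five parts.

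- **The rule is disclosed.** It is stated in SAP 2.4, repeated in SAP 6 and fixed in advance. That stands: a reader might infer a hidden test, but the documents do not support this. The objection is to what the rule does.
- **Much lower-dose information remains.** SAP 6.3 plots survival curves by dose, 6.4 tabulates counts with means and SDs by group, Section 7 tabulates adverse events, and SAP 6 adds a pooled NR comparison. This stands too. A reader might infer that harm at the lower doses would go unreported; the documents do not say that. From the count tables one could even rebuild a Welch interval, apart from the imputation for deaths. None of these outputs, however, is a planned effect estimate with CI at 500 or 250 mg/day.
- **The coverage loss is limited.** The 85% applies to the 5% of no-effect trials in which the gate opens; the interval is both shown and wrong in only about 0.8% of such trials. The upward shift of 0.18 to 0.19 SD is about half of one SE (0.39). Both are correct, and undercoverage hardly reaches mortality. Absence of the estimate is the larger problem.
- **Monotonicity may be reasonable.** The protocol synopsis expects NR to reduce complications, morbidity and mortality, so these outcomes are also hoped-for benefits. That supports an ordering for benefit; the SAP gives no reason for one under a safety heading.
- **The grip-strength gate is clear enough.** A reader might think it undefined, because one model yields a day-7 and a day-90 interval. The outcome table in SAP 5 and the text of 6.2 list them as separate outcomes, so one gate for each is the natural reading.

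**Conclusion.** The point holds as a reporting weakness that should be corrected; it does not touch the primary conclusion. That the gate applies to all secondary outcomes, and that it protects no declared error rate, follows from the text alone.

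Its size depends on assumptions. For a normal outcome with no effect, the 500 mg/day estimate appears in about 5% of trials and the 250 mg/day estimate in about 0.8%. With 0.5 SD true at both higher doses, the 500 mg/day estimate appears in 32% and is inflated to about 0.69 SD. For mortality the HR at 500 mg/day is mostly missing: about 0.1, 1 and 3% of trials produce it with no effect, and 1, 8 and 22% with an HR of 2 at 1 g/day, at assumed placebo mortality of 10, 17 and 30% with common follow-up.

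**What to change.** Keep the ordered steps for the primary test only. Replace the last sentence of Adaptation to Estimation in SAP 2.4, and align the introduction to SAP 6, with:

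> For every secondary outcome the estimated difference or ratio v placebo with 95% CI will be reported for each of the three doses, whatever the other doses show; these are descriptive and not adjusted for multiplicity.

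For grip strength, report both the day-7 and the day-90 difference at each dose.

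Where a group has no deaths, the Cox HR cannot be estimated. The chance of this in a group of 10 is 0.90^10 = 35%, 0.83^10 = 16% or 0.70^10 = 3% at 10, 17 or 30% mortality. In that case say so, and report deaths and person-time in that group and in placebo, with a comparison that allows for follow-up time, such as an exact CI for the rate ratio. A single-arm proportion would not do: it is not a comparison with placebo, and the doses were enrolled in successive phases, so follow-up may differ.

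The costs are a few table rows and the following.
- **Wide intervals in the groups of 10.** At 17 to 30% mortality the HR is typically divided or multiplied by about 7 to 4.
- **More intervals that exclude the null by chance.** With no effect, the chance that at least one dose CI does so rises from about 5% to about 13% per normal or count outcome, and from 1–3% to 2–6% for mortality at 17 to 30%. Across the five secondary outcomes, treated as independent for illustration and with mid-range mortality values, it rises from 1 − 0.95^4 × 0.98 = 20% to 1 − 0.87^4 × 0.96 = 45%. The descriptive label is there for this reason.

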2.5 Statistical Interim Analyses and Stopping Guidance

There is no interim analysis of efficacy in this study.

The Data Monitoring Committee (DMC) will recommend stopping the trial if there is a safety concern. There is a separate DMC Charter detailing the procedures for the DMC.

2.6 Timing of Final Analysis

The main analysis is planned to after patients have concluded 90 days of treatment and attended the 65 weeks follow-up appointment. All data will be entered, verified and validated before the primary database will be locked, un-blinded and data analysis commenced.

2.7 Timing of Outcome Assessments

The target days and visits windows are defined in the protocol as:

Target Day	Definition (Day window)	
-14	Two weeks prior to acute	
	admission to hospital	
Day 1 (Randomization)	Day 1	
Day 3	Target day -1 day/+2 days	
Day 7, 14, 21, 28	Target day± 3 days	
Day 30	Target Day ±10 days	
Day X	Discharge date ± 0 days	
Day X	Withdrawal date ± 0 days	
Day X	Death date ± 0 days	
Day 90	Target day + 90 days/-30days.	
65 weeks	Target day +/-180 days.	
	-14 Day 1 (Randomization) Day 3 Day 7, 14, 21, 28 Day 30 Day X Day X Day X Day X Day 90	

3 Statistical Principles

3.1 Confidence Intervals and P-values

All calculated *P*-values will be two-sided and compared to a 5% significance level. If a *P*-value is less than 0.05, the corresponding treatment group difference will be denoted as statistically significant. All efficacy estimates will be presented with two-sided 95% confidence intervals. The statistical approach to account for multiple testing of three doses versus placebo is the closed multiple test procedure (see Section 2.4). As there is only one primary null hypothesis setup to be tested in this trial, there will be no further adjustments for multiplicity.

3.2 Adherence and Protocol Deviations

Adherence to Allocated Treatment

Compliance from inclusion to discharge is defined by administrations recorded in hospital records. Post discharge compliance is determined by self-reported compliance. In addition, results from counting of returned capsules will be reported. Compliance is furthermore assessed based on the percent of subjects who have taken the scheduled number of pills and measurements of NR metabolites that will be available only after unblinding.

Compliance is defined as:

% compliance = (number of days the study drug was taken/ number of days the study medicine was supposed to have been taken.

A patient will be defined as non-compliant if compliance is less than 75% during the hospital stay.

Protocol Deviations

The following are pre-defined major protocol deviations regarded to affect the efficacy of the intervention:

- Entering the trial when the eligibility criteria should have prevented trial entry
- Non-compliance (defined above)
- Diagnosed cancer, or meeting other exclusion criteria, during the treatment period

Protocol deviations are classified prior to unblinding of treatment. The number (and percentage) of patients with major and minor protocol deviations will be summarized by treatment group with details of type of deviation provided. The patients that are included in the Full Analysis Set (see Section 3.4) will be used as the denominator to calculate the percentages. No formal statistical testing will be undertaken.

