#### 4.4 **Exclusion criteria**

- Exclusion Criteria 1. Allergy to NR or ingredients in capsules or placebo.
  - 2. Patients expected to pass away within 90 days.
  - 3. Patients unable to give their consent
  - 4. Unstable patients:

- i. Uncontrolled infection (clinical septicaemia, inadequate response to treatment, inadequate control of source of infection or at treating physician's discretion).
- ii. MAP < 70 mm Hg and symptoms of hypotension.
- iii. Patients requiring dialysis at the time of inclusion or GFR <25
- iv. Liver failure with Child-Pugh class B or C or any class associated with hepatic encephalopathy (any grade), ALT or AST >3 times upper limit. If liver transaminases are elevated for other reasons than hepatocyte damage, patients may be included regardless of ALT/AST values \*
- v. Severe peripheral oedema and/or pulmonary oedema, any unstable cardiac rhythm, ongoing myocardial ischemia, troponin T >500.
- vi. Signs of elevated intracranial pressure (headache, vomiting and depressed global consciousness in conjunction with focal neurological signs, papilledema, spontaneous periorbital bruising and a triad of bradycardia, respiratory depression and hypertension).
- vii. Arterial pH <7.30 or >7.50
- viii. Serum potassium under 3, 2 or over 5 mmol/L.
- 5. Pregnancy or breastfeeding \*\*
- 6. Any cancer not in full remission for >10 years (for non-melanoma skin cancers, full remission for >1 year)
- 7. Use of St John's Wort based supplements during the past 30 days
- 8. Patient has undergone solid organ transplantation
- 9. Participation in any clinical trial with unknown medications
- 10. Major gastrointestinal or other major internal bleeding past 2 days.
- 11. Logistical challenges after discharge. Patient must be able to attend follow up.
- 12. Intracerebral haemorrhage or major stroke past week.
- 13. The treating physician considers the patient unfit or unable to participate.
- \*Please also see Amendment number 1.
- \*\* All fertile women must have an HCG test.

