3.4 Analysis Populations

The Enrolled set will include all patients who have provided informed consent and have been included into the study data base.

The Full Analysis Set (FAS) will be defined as all patients randomly assigned to a treatment group having received at least one dose of study medication.

The Safety Analysis Set (SAS) will include all patients having received at least one study medication. Subjects who withdraw from the study will be included in the SAS. A list of withdrawn subjects, with the reasons for withdrawal, will be made.

The Per Protocol Analysis Set (PPS) will include all randomised patients meeting the study eligibility criteria, with no major protocol deviations affecting the treatment efficacy, and who are compliant for the study drug.

4 Trial Population

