6.1 Primary Outcome

The primary outcome is length of hospital stay (time to discharge), measured in number of days, and the primary analysis of the primary outcome will be performed on the full analysis set (FAS). A secondary (sensitivity) analysis of the primary outcome will be performed on the per protocol set (PPS).

Statistical Method for Steps 1-3

The comparison of the length of hospital stay between the NR and placebo groups – in each of the three steps – will be carried out with a Weibull survival model, with time as the number of days of hospital stay and treatment (NR vs placebo) as explanatory variable. The estimated treatment effect will be the hazard ratio (HR) for treatment with a 95% confidence interval.

Presentation of Results

The estimated treatment effect (HR) with a 95% confidence interval will be presented, together with the P-value for the null hypothesis of a zero-treatment difference (HR = 1).

The observed mean and standard deviation for placebo and each dose will be presented in a figure, along with the observed values (length of hospital stay) for each individual, as a scatter with connected lines-plot. Figure 1 shows an example with simulated data.

A plot of the Kaplan-Meier survivor function (for time to discharge) of each dose and placebo will be presented.

[figure not shown]

Figure 1: Simulated data

Missing Data

We will have complete data on the length of hospital stay, except for the following situation: A patient dies before being discharged from the hospital. In this case, the patient will be censored at the time of death. Imputation of the length of hospital stay will be performed as a sensitivity analyses (see item 3 below).

Sensitivity Analyses

The following sensitivity analyses will be performed on the primary outcome:

- 1. As described above but on the per protocol set (PPS)
- 2. As described above but with Cox proportional hazard regression instead of Weibull regression
- As described above but with Cox proportional hazard regression and imputation (instead of censoring) of the length of hospital stay with the maximum length of hospital stay (regardless of treatment group) for patients who die before discharge

Subgroup Analyses

There will be no subgroup analyses.

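### The per-protocol set drops patients who meet an exclusion criterion after randomisation, so the first sensitivity analysis of length of stay selects on clinical events that treatment may affect

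*SAP*

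**What the plan says.** SAP 3.2 lists three major deviations that it regards as affecting the efficacy of the intervention: entering the trial while ineligible, non-compliance (below 75% during the hospital stay), and "Diagnosed cancer, or meeting other exclusion criteria, during the treatment period". Ineligible entry has its own bullet, so the third bullet can only refer to what happens after randomisation.

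SAP 3.4 limits the per-protocol set (PPS) to eligible randomised patients "with no major protocol deviations affecting the treatment efficacy, and who are compliant for the study drug". SAP 3.2 has already declared its list to affect efficacy, so nothing in 3.4 lets these patients back in. SAP 6.1 runs the primary analysis of length of stay on the full analysis set (FAS) and uses the PPS for sensitivity analysis 1.

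The exclusion criteria in Protocol 4.4 include a group headed as unstable patients. Among them are "Uncontrolled infection (clinical septicaemia, inadequate response to treatment, inadequate control of source of infection", "MAP < 70 mm Hg and symptoms of hypotension", a GFR below 25, arterial pH outside 7.30 to 7.50, and "Serum potassium under 3, 2 or over 5 mmol/L" (read here as 3.2). Protocol 3 sets treatment at three months. Protocol 6.1 schedules inpatient laboratory tests on days 1, 3 and 7 and weekly after that, then at day 90.

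**The concern.** A patient who becomes septic or hyperkalaemic on day 10 has not departed from the protocol; this is part of the course of the illness. Removing that patient conditions the comparison on an event that follows randomisation, that NR might cause or prevent, and that may itself lengthen the stay. The arms that remain are no longer the arms that were randomised.

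Two features of the schedule add to this.

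- **Longer stays are checked more often.** A patient discharged on day 10 has two scheduled inpatient tests after baseline (days 3 and 7). One still in hospital on day 21 has four (days 3, 7, 14 and 21).
- **Most of the treatment period falls after discharge.** With the planned median stay of 15 days, about 90 − 15 = 75 of the 90 days come after the primary outcome is known. An out-of-range potassium at day 90 would still remove the patient from an analysis of a stay that it could not have influenced.

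At stake is whether sensitivity analysis 1 shows what a per-protocol analysis should show. If NR shortens or lengthens stay by changing the complication rate, the rule removes the patients in whom that effect appears.

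**Working it through.** **Inputs from the documents.** Length of stay is Weibull with scale 18 and shape 2.2, and the largest reduction is 33% (SAP 2.3). Step 1 compares 20 patients on 1 g/day with 18 on placebo (SAP 2.1, 2.4). Tests are two-sided at 5% (SAP 3.1). The model is a Weibull proportional-hazards model (SAP 6.1).

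**Assumed input.** The documents give no rate at which patients meet a criterion after randomisation. I take 1% to 4% per inpatient day, in-hospital events only, and no censoring for death.

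**1. The plan's own figures.** The median is 18 × (ln 2)^(1/2.2) = 15.2 and the quartiles are 10.2 and 20.9, against the stated 15 and 10 to 21. A multiple-contrast test on log stay, with variance 1/(2.2² × n) and effect −ln 0.67, gives 79% power at one-sided 2.5%, against the stated 80% or so. The curve parameters are not stated; I assumed an ED50 of 100 to 500 mg and an exponential delta of 300 to 500 mg. These figures do not depend on the PPS rule.

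**2. Step 1 without the rule.** The hazard ratio (HR) for discharge is 0.67^(−2.2) = 2.41. With all 38 patients discharged, √(38 × 20/38 × 18/38) × ln 2.41 − 1.96 = 0.75, which is 77% power. Simulation gives 76%.

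**3. Step 1 with the rule.** A patient is kept with probability exp(−h × stay), with the same h in both arms and a true 33% reduction.

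| h per inpatient day | Dropped, placebo / NR | Large-sample HR | Step 1 power |
|---|---|---|---|
| 0 | 0 / 0 | 2.41 | 76% |
| 1% | 14% / 10% | 2.32 | 67–68% |
| 2% | 27% / 19% | 2.24–2.25 | 58–59% |
| 3% | 37% / 27% | 2.18 | not run |
| 4% | about 8 of 18 / 7 of 20 | about 2.09 | 41–44% |

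At 1% to 3% per day, dropped placebo patients stayed about 19 days on average; those kept stayed 14.3 to 15.4.

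**4. How much of the power loss is bias.** At 2% per day, dropping the same number of patients at random already lowers power from 76% to about 65%. That is 11 of the 18 points lost. At 4% the random drop gives about 55% against 44% with the rule, so 21 of 32 points. Roughly 60% to 65% of the loss is simply fewer patients.

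**5. Other assumptions about the events.**

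- Event unrelated to stay (20% in each arm): HR 2.42 with and without the rule.
- No treatment effect, equal rates: HR 1.00.
- No treatment effect, 2% per day in one arm and 1% in the other: HR 0.93 if placebo has the higher rate, 1.07 if NR has. Step 1 rejection is about 7%, against 6% with no exclusions.
- The complication lengthens stay by 50%, and NR acts only by halving it (30% to 15%): HR 1.16 in the FAS, 1.00 in the PPS. If NR doubles it (15% to 30%): 0.86 in the FAS, 1.00 in the PPS.
- The complication lengthens stay by 50% equally in both arms (20%), with a direct 33% effect of NR: 2.23 in the FAS, 2.41 in the PPS.

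So the shift can be towards the null, away from it, or absent.

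**The case against.** The strongest reply is that little depends on this analysis. SAP 2.4 names one primary analysis and treats all other efficacy analyses as supportive or exploratory. The stepwise dose decision does not use the PPS. Deviations are classified before unblinding and tabulated by arm and type, so an imbalance would be visible. Every per-protocol set selects on something after randomisation, compliance included. All of this stands, and it limits the weight of the point. Blinding, however, only prevents biased judgement; it does not stop selection on an event that treatment has changed.

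A second reply is that the rule covers 90 days for everyone. If the risk were constant over that period, removal would be unrelated to stay and no bias would follow. That is correct. The link to stay is plausible, because instability and laboratory checks are concentrated in hospital, but its strength is assumed.

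A reader might go further in three ways that the documents do not support.

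- **That the primary result is compromised, because Protocol 10.3 calls the per-protocol population primary.** SAP 6.1 uses the FAS, and the Protocol's population is defined by more than 30 days of dosing, without this rule. The two documents should be reconciled, but that is a separate matter.
- **That the analysis must lose more long-stay placebo patients and so cannot support the primary result.** Neither the size nor the direction is fixed by the documents.
- **That every criterion can be triggered later.** Dialysis is tied to the time of inclusion, low MAP needs symptoms, and raised transaminases are exempt when hepatocyte damage is not the cause.

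**Conclusion.** The point holds for one supportive analysis. As written, the PPS removes patients for complications that arise after randomisation, including after the outcome is known, and there is no per-protocol reason to do so for this endpoint. At the assumed rates with a true 33% reduction the HR bias is modest. The more serious possibility is that an effect of NR, good or bad, that works only through complications would disappear from the PPS. The power figures should not be read as a measure of bias. The FAS analysis and the minimum-effective-dose conclusion stand as planned. This is a cheap improvement worth considering, not a flaw in the trial's main inference.

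**What to change.** Replace the third bullet of the deviation list in SAP 3.2, so that major deviations for the PPS are:

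- (a) eligibility violations already present at randomisation;
- (b) non-compliance as SAP 3.2 defines it;
- (c) use of a product that the protocol prohibits (St John's Wort, Protocol 5.4) between the first dose and the end of the index stay.

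State that patients with a new cancer diagnosis or clinical instability after randomisation remain in the PPS, and report those events under safety in SAP 7. Replace the whole bullet: deleting only the words on exclusion criteria and the treatment period would leave a cancer diagnosis as a deviation with no time window, and would lose prohibited-product use.

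The cost is one bullet of text, and Protocol 10.4 allows changes to the plan until database lock. The small downside is that the PPS will include some patients whose later illness dilutes a pure on-treatment effect. The set will still select on compliance, so it should continue to be read as supportive.
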